3.5 Blinding

Participants, study staff and study investigators are blinded to treatment group allocation. Data analysts will necessarily be unblinded while performing the analysis.

3.6 Sample size

To detect a clinically meaningful difference of 40 µg/L in human milk total thiamine concentration between any two treatment groups with 90% power, assuming a SD of 43 µg/L (estimated SD of control group in a Cambodian thiamine-fortified fish sauce trial^[1]) 48 women are required per treatment group, or a total of 192 women. This sample size allows for 20% attrition and is based on a two-sided alpha of 0.0083 for each of the 6 pairwise comparisons between 4 treatment groups to maintain an overall alpha of 0.05. Recruitment of 320 participants (80 per group) was planned to allow for some uncertainty in the assumed values, particularly the SD which may be larger than anticipated.

Simulations of 500 dose-response curves for human milk total thiamine concentration were conducted to estimate the precision that this sample size would provide for addressing the primary study objective (i.e. for estimating the dose required to achieve 90% of the average maximum human milk total thiamine concentration). Data were simulated based on an average minimum and maximum concentration of 136 µg/L^[1] and 210 µg/L^[2] respectively, with a SD of 43 µg/L^[1], and reaching 50% and 90% of the maximum average concentration at dose 1.2 mg/d (EAR group) and 2.4 mg/d (double EAR group) respectively. Assuming a dose-response Emax curve, the precision of the estimated dose is ±1.29 mg/d (i.e. the 95% confidence interval for the estimated dose will be within ±1.29 mg/d of the point estimate).

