Simulations of 500 dose-response curves for human milk total thiamine concentration were conducted to estimate the precision that this sample size would provide for addressing the primary study objective (i.e. for estimating the dose required to achieve 90% of the average maximum human milk total thiamine concentration). Data were simulated based on an average minimum and maximum concentration of 136 $\mu\text{g}/\text{L}$ (9) and 210 $\mu\text{g}/\text{L}$ (1), respectively, with a SD of 43 $\mu\text{g}/\text{L}$ (9), and reaching 50% and 90% of the maximum average concentration at dose 1.2 mg/d (EAR group) and 2.4 mg/d (double EAR group) respectively. Assuming an Emax dose-response curve, the precision of the estimated dose is ± 1.29 mg/d (i.e. the 90% confidence interval for the estimated dose will be within ± 1.29 mg/d of the point estimate).

8. Enrolment and Randomization

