7 STATISTICAL ANALYSES

In this section, the following details are provided for each outcome variable that will be analysed to address the study objectives specified in Section 2:

- **Outcome:** A detailed description of the outcome variable, including the type of variable and how it will be calculated (if applicable).
- **Analysis:** The type of statistical analysis to be performed and parameters to be estimated.
- **Adjustment:** Where relevant, the covariates at 2 weeks postnatal (stratification variables and potential confounders) to adjust for in the adjusted analysis.

For each outcome variable, parameter estimates will be accompanied by 95% two-sided confidence intervals and statistical significance will be assessed at the 0.05 level using a two-sided test, unless otherwise specified.

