7.1 Emax curve

Analysis of the primary and several secondary outcomes will be based on the Emax curve.

The Emax curve is defined as:

$$Y = E_0 + E_{\max} \left(\frac{\text{dose}^h}{ED_{50}^h + \text{dose}^h} \right)$$

where E_0 is the baseline concentration without supplementation, E_{\max} is the maximum effect of supplementation, ED_{50} is the dose that produces half of the maximum effect of supplementation and corresponds to the inflection point at which the effectiveness of higher doses starts to decrease, and h is the slope or Hill factor.

The nonlinear Least squares model for the primary outcome will be formulated as:

$$Y = E_0 + E_{\max} \frac{\text{dose}^h}{ED_{50}^h + \text{dose}^h} + \epsilon$$

For secondary outcomes involving testing for effect modification by presence or absence of genetic hemoglobin disorder (GD), additional coefficients (α , β , γ and δ) will be added to all parameters of the Emax curve. The model will be formulated as:

$$Y = (E_0 + E_0\beta\text{GD}) + (E_{\max} + E_{\max}\gamma\text{GD}) \frac{\text{dose}^{(h+h\delta\text{GD})}}{(ED_{50} + ED_{50}\alpha\text{GD})^{(h+h\delta\text{GD})} + \text{dose}^{(h+h\delta\text{GD})}} + \epsilon$$

Evidence of curve shape differences between presence or absence of genetic hemoglobin disorder will be determined by global Likelihood ratio tests. Further testing of the four additional coefficients, in the form of H_0 : coefficient = 0, will be conducted following evidence ($P < 0.05$) from the global test.

The parameter of interest for this study is the dose required to achieve 90% of the maximum concentration (i.e. 90% of $E_0 + E_{\max}$) and this will be estimated from the fitted Emax curve with variance estimated from non-parametric bootstrapping of 100 resamples. For outcomes where there is evidence of curve difference by genetic hemoglobin disorder status ($P < 0.05$ for likelihood ratio test), separate estimates for the dose required to achieve 90% of the maximum concentration with and without genetic hemoglobin disorder will be reported.

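### The one precision figure for the primary dose estimate, ±1.29 mg/d, is a 90% interval in the protocol and a 95% interval in the SAP, and the scenario behind it is misworded

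*Combined protocol and SAP*

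**What the plan says.** Protocol section 7 (Sample Size) and SAP section 3.6 describe the planning simulation for the primary objective with identical inputs: 500 simulated curves, mean milk thiamine running from 136 to 210 µg/L, SD 43 µg/L, and an Emax shape "reaching 50% and 90% of the maximum average concentration at dose 1.2 mg/d (EAR group) and 2.4 mg/d (double EAR group) respectively". Both give ±1.29 mg/d as the result.

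They differ on what that number is. The protocol says "the 90% confidence interval for the estimated dose will be within" that margin. The SAP says "the 95% confidence interval for the estimated dose will be within ±1.29 mg/d of the point estimate".

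The level of the real analysis is not in doubt. SAP section 7 says "parameter estimates will be accompanied by 95% two-sided confidence intervals", and SAP 7.2.1 and protocol section 11 also name 95% for the dose estimate.

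SAP 7.1 defines ED50 on the effect scale (it "is the dose that produces half of the maximum effect of supplementation"), while the target dose is the one giving 90% of E0 + Emax, which is on the concentration scale. The exponent h "is the slope or Hill factor" and has no stated value.

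On numbers, SAP 3.6 says "Recruitment of 320 participants (80 per group) was planned to allow for some uncertainty in the assumed values". The attrition allowance belongs to the pairwise calculation of 48 per group: "This sample size allows for 20% attrition and is based on a two-sided alpha of 0.0083".

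**The concern.** One half-width from one simulation cannot be both a 90% and a 95% half-width. Both statements are current text, since the SAP is Appendix B of the protocol, so this is not a difference between a superseded and a live version.

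The figure matters because it is the only precision given for the primary objective. The power calculation concerns pairwise differences in mean concentration, which is a secondary analysis. A reader judging how well four doses can locate the 90% dose has only ±1.29 mg/d, and cannot tell its confidence level.

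The scenario wording adds to this. Taken literally, its 50% point lies below the concentration at zero dose, so the simulation cannot be rebuilt from the text to find out which label is correct.

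**Working it through.** **1. What the label is worth**

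- If 1.29 is a 90% half-width: SE = 1.29/1.645 = 0.784, and the 95% half-width = 1.96 × 0.784 = 1.54 mg/d. Ratio 1.54/1.29 = 1.19.
- If 1.29 is a 95% half-width: SE = 1.29/1.96 = 0.658, and the 90% half-width = 1.645 × 0.658 = 1.08 mg/d.

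This scaling assumes a roughly normal estimate. The estimated dose is skewed to the right, so 1.54 is approximate and should not be turned into exact limits around 2.4 mg/d.

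**2. The 50% and 90% points** (136 and 210 µg/L from SAP 3.6, so Emax = 210 − 136 = 74)

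- 50% of the maximum concentration: 0.5 × 210 = 105 µg/L, which is 31 below the minimum of 136. No curve rising from 136 to 210 passes through it.
- 50% of the effect: 136 + 0.5 × 74 = 173 µg/L, which is attainable and matches the SAP 7.1 definition of ED50.
- 90% of the maximum concentration: 0.9 × 210 = 189 µg/L, which is attainable and is the SAP 7.1 target. As a fraction of the effect it is (189 − 136)/74 = 0.716.

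Two readings can be built:

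- *Mixed scales* (50% of effect at 1.2 mg/d, 90% of concentration at 2.4 mg/d): h = ln(53/21)/ln 2 = 1.34. Arm means are 136, 173, 189 and 205.9 µg/L, and the target falls at 2.40 mg/d.
- *Both on the effect scale*: h = ln 9/ln 2 = 3.17. The mean at 2.4 mg/d is 136 + 0.9 × 74 = 202.6 µg/L, and the SAP 7.1 target of 189 µg/L is reached at 1.2 × (53/21)^(1/3.17) = 1.61 mg/d, not 2.4. With h fixed at 3.17 and 80 per arm, 95% half-widths are only about 0.3 to 0.5 mg/d, so this reading does not give 1.29.

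**3. Can ±1.29 be reproduced, and at which level?**

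Take the mixed-scale curve with h fixed at 1.34. The target dose is ED50 × [(0.9·Emax − 0.1·E0)/(0.1·(E0 + Emax))]^(1/h). Two inputs are assumptions, because the documents do not give them: that h was fixed, and the number analysed per arm. For the latter I use 80 (all recruited) and 80 × 0.8 = 64 (a 20% loss, carried over from the pairwise calculation).

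The delta method uses variance 43²/n for each arm mean. The simulation uses 40,000 trials, least squares and percentile half-widths; brackets show the 95% range that a run of 500 curves would give.

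| Analysed per arm | SE (delta) | 90%, delta | 95%, delta | 90%, simulated | 95%, simulated |
|---|---|---|---|---|---|
| 80 | 0.659 | 1.08 | 1.29 | 1.12 (1.02–1.22) | 1.36 (1.23–1.49) |
| 64 | 0.736 | 1.21 | 1.44 | 1.27 (1.15–1.38) | 1.54 (1.39–1.69) |

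Against the brackets, 1.29 is compatible with 95% at 80 per arm and with 90% at 64 per arm. It is outside the range for 90% at 80 and for 95% at 64.

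**The case against.** **The 50% point is loose wording, not a design fault.** This stands. SAP 7.1 defines ED50 as half of the effect, so the intended point can be recovered, and nothing shows that the simulation itself used an impossible curve. What remains is that one phrase covers two percentages that only fit the SAP target if they sit on different scales, and the text does not say so.

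**The figure is descriptive.** This also stands. The 48 per group comes from the pairwise calculation, the 80 per group is justified by uncertainty about the SD, and the trial will report its own bootstrap interval. A reader might infer that the sample size is wrong or the trial too small. The documents do not support that.

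**The SAP label can be shown to be right.** A reader might infer this because the delta method at 80 per arm gives 1.29 at 95%. It does not follow. Both documents say the figure came from simulation, and neither mentions the delta method. Among the simulated values the nearest to 1.29 is 1.27 (90%, 64 per arm) rather than 1.36 (95%, 80 per arm). Nor does that prove the protocol label, since 64 is an assumption and 1.29 lies within the range of a 500-curve run for both.

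**The true precision must be far worse because h will be estimated.** SAP 7.1 does read as estimating h: it is written as a parameter, and the genetic-disorder model adds a coefficient to it. Four parameters on four doses is a saturated fit, so precision could well be poorer than with h fixed. But any half-width quoted for that case depends on bounds placed on h, which the documents do not give. I therefore put no number on it.

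**Conclusion.** The inconsistency is real and needs no assumptions: the same ±1.29 mg/d carries two confidence levels, and at least one is wrong. If the protocol's 90% is correct, the 95% half-width is roughly ±1.54 mg/d and SAP 3.6 understates it, the true figure being about 19% larger. If the SAP's 95% is correct, only the protocol needs changing. The documents do not decide between these. The compatibility of 1.29 with either label rests on the mixed-scale curve, a Hill factor fixed at 1.34, and 80 or 64 analysed per arm.

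The scenario wording is wrong as it stands (105 < 136 µg/L). Putting both points on the effect scale does not repair it, because the SAP target then moves to about 1.61 mg/d.

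Confidence is high for the label conflict and for the 105 µg/L arithmetic. It does not extend to which label is right. The point should be fixed, but its reach is limited to the stated planning precision.

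**What to change.** 1. Check the simulation record. In protocol section 7 and SAP 3.6, give the same 95% half-width, to match the planned analysis.
2. In both places, restate the 50% and 90% points on named scales (effect or concentration), with E0, Emax, ED50, the Hill factor and whether it was fixed or estimated, and the number analysed per arm.
3. If the record does not confirm a 95% level under the SAP 7.1 model, rerun the simulation with that model for the dose giving 90% of E0 + Emax, and replace ±1.29 in both documents. If the team prefers to fix h in SAP 7.1 instead, the genetic-disorder model, which lets h vary, has to be revised too.

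Cost: at best, one corrected level in one document and clearer inputs in both; otherwise one simulation rerun. The stated precision may become less favourable. The sample size, the arms and the 95% level of the final interval do not change.

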4 SEQUENCE OF PLANNED ANALYSIS

4.1 Interim analysis

There are no planned interim analyses for this study.

4.2 Final analysis and reporting

Once data collection and cleaning is complete, the database will be locked and unblinded treatment codes will be included in the database; a blinded analysis is not possible for estimating dose response curves.

Due to the time-consuming nature of coding video-recorded cognitive assessments, data for the following assessments will not be included in the database before it is locked and unblinded: primary engagement task, secondary engagement task, Visual Paired Comparison Task, and Language Preference Task. Note that the research assistants coding the videos for these assessments will remain blinded.

Analysis of all primary and secondary outcomes will be performed as described in this SAP and the results of the statistical analyses will be made available to the Principal Investigator.

Any post-hoc, exploratory analyses which were not specified in this SAP will be clearly identified in the final report.

5 GENERAL ISSUES FOR STATISTICAL ANALYSIS

5.1 Analysis software

All analyses will be performed using R version 3.4.4 or later.

5.2 Analysis approach

The primary analyses will be performed using an intention-to-treat (ITT) approach, where analyses will be conducted according to the randomised treatment group regardless of participants' compliance with the protocol. Secondary 'per-protocol' analyses will be performed including only women who consumed $\geq 80\%$ capsules over the 22-week intervention period.

5.3 Methods for withdrawals, missing data and outliers

All available data collected up until time of withdrawal will be included in the statistical analysis.

Multiple imputation using chained equations will be performed separately by randomised treatment group to address missing data under a missing at random assumption. A total of 100 imputations will be performed to ensure $<1\%$ loss of power compared to full information maximum likelihood^[3]. Covariates pre-specified for adjustment in the analysis will be included in the imputation model, along with other auxiliary variables useful for improving the prediction of missing values. Conclusions will be based on the results obtained using imputed data, with sensitivity analyses performed on unimputed data.

Outliers will not be excluded from the primary analysis unless a data entry error is confirmed.

5.4 Protocol violations and deviations

No participants will be excluded from the primary intention-to-treat analyses due to protocol deviations.

For the secondary 'per-protocol' analyses, only women who consumed $\geq 80\%$ capsules over the 22-week intervention period will be included.

5.5 Data transformations

No data transformations are planned. The statistical analyses detailed in Section 7 are based on assumptions about the distribution of the outcomes. If these assumptions turn out to be invalid, data transformations may be required. Log transformation is expected to be required for analysis of Oculomotor score.

5.6 Covariates for adjustment

Both unadjusted and adjusted analyses will be performed for some outcomes. Conclusions for these outcomes will be drawn from the adjusted analyses, with unadjusted analyses performed for completeness and to potentially confirm the results of the adjusted analyses.

All adjusted analyses will be adjusted for health centre, since it was used as a stratification variable in the randomisation process. Adjustment will also be made for additional variables collected at 2 weeks postnatal which are potential confounders for some outcomes and these have been identified a priori (see Section 7).

If convergence is an issue, some potential confounders may be excluded from the adjusted analysis. Any deviation from the planned adjustment covariates will be documented in the final report.

5.7 Planned subgroup analyses

For the secondary outcomes of maternal and infant ThDP and TKac, secondary analyses will be performed to test for evidence of effect modification by presence/absence of genetic hemoglobin disorder.

Analysis of secondary outcomes on Mullen, VPC Novelty Scores, Language Preference Task scores, and oculomotor scores will be performed in a subset of women comparing only those who were assigned to receive 0 mg/d (placebo) to those who were assigned to receive 10 mg/d (positive control) of thiamine.

5.8 Multiple comparisons and multiplicity

[figure not shown]
Since there is only one primary outcome for the trial and less importance will be placed on the results of the secondary outcomes and the secondary analyses testing for interactions, no adjustment will be made for multiple outcomes and analyses being performed.

Since conclusions will be drawn based on the adjusted results (where performed) using the imputed data, no adjustment will be made for the fact that both adjusted and unadjusted analyses are being performed (where applicable) on both raw and imputed datasets.

For secondary outcomes where the objective of the analysis is to compare the four treatment groups, multiple comparisons will be addressed by first testing whether there is any evidence of a treatment group effect. Where this test reaches statistical significance ($P < 0.05$), post-hoc tests will be performed to test for differences between each pair of treatment groups and Tukey's honestly significance difference (HSD) will be used to control the type I error rate across the 6 pairwise tests.

6 DESCRIPTIVE STATISTICS

6.1 Participant flow

6.2 Baseline characteristics (2 weeks postnatal)

A descriptive comparison of the randomised groups will be conducted on all baseline characteristics in the 2 weeks postnatal questionnaire. Iron biomarkers ferritin and soluble transferrin receptor, vitamin A marker retinol binding protein, and C-reactive protein (CRP) and α -1-acid glycoprotein (AGP) at baseline will also be included. Means and standard deviations, or medians and interquartile ranges will be reported for continuous variables. Frequencies and percentages will be reported for categorical variables.

6.3 Measurement of treatment compliance

Treatment compliance will be assessed descriptively by treatment group based on the number of unused capsules (Module 1.2 from Fortnightly monitoring data collection sheet) counted every fortnight over the 22 week intervention period.

6.4 Missing data

Missing data will be assessed descriptively by treatment group for each outcome variable and potential confounder.

6.5 Randomisation errors

Information listed below will be summarised descriptively by treatment group:

- Number of mothers randomised in the wrong stratum
- Number of mothers given the wrong treatment
- Number of mothers discovered to be ineligible after randomisation

7 STATISTICAL ANALYSES

In this section, the following details are provided for each outcome variable that will be analysed to address the study objectives specified in Section 2:

- **Outcome:** A detailed description of the outcome variable, including the type of variable and how it will be calculated (if applicable).
- **Analysis:** The type of statistical analysis to be performed and parameters to be estimated.
- **Adjustment:** Where relevant, the covariates at 2 weeks postnatal (stratification variables and potential confounders) to adjust for in the adjusted analysis.

For each outcome variable, parameter estimates will be accompanied by 95% two-sided confidence intervals and statistical significance will be assessed at the 0.05 level using a two-sided test, unless otherwise specified.

7.1 Emax curve

Analysis of the primary and several secondary outcomes will be based on the Emax curve.

The Emax curve is defined as:

$$Y = E_0 + E_{\max} \left(\frac{\text{dose}^h}{ED_{50}^h + \text{dose}^h} \right)$$

where E_0 is the baseline concentration without supplementation, E_{\max} is the maximum effect of supplementation, ED_{50} is the dose that produces half of the maximum effect of supplementation and corresponds to the inflection point at which the effectiveness of higher doses starts to decrease, and h is the slope or Hill factor.

The nonlinear Least squares model for the primary outcome will be formulated as:

$$Y = E_0 + E_{\max} \frac{\text{dose}^h}{ED_{50}^h + \text{dose}^h} + \epsilon$$

For secondary outcomes involving testing for effect modification by presence or absence of genetic hemoglobin disorder (GD), additional coefficients (α , β , γ and δ) will be added to all parameters of the Emax curve. The model will be formulated as:

$$Y = (E_0 + E_0\beta\text{GD}) + (E_{\max} + E_{\max}\gamma\text{GD}) \frac{\text{dose}^{(h+h\delta\text{GD})}}{(ED_{50} + ED_{50}\alpha\text{GD})^{(h+h\delta\text{GD})} + \text{dose}^{(h+h\delta\text{GD})}} + \epsilon$$

Evidence of curve shape differences between presence or absence of genetic hemoglobin disorder will be determined by global Likelihood ratio tests. Further testing of the four additional coefficients, in the form of H_0 : coefficient = 0, will be conducted following evidence ($P < 0.05$) from the global test.

The parameter of interest for this study is the dose required to achieve 90% of the maximum concentration (i.e. 90% of $E_0 + E_{\max}$) and this will be estimated from the fitted Emax curve with variance estimated from non-parametric bootstrapping of 100 resamples. For outcomes where there is evidence of curve difference by genetic hemoglobin disorder status ($P < 0.05$ for likelihood ratio test), separate estimates for the dose required to achieve 90% of the maximum concentration with and without genetic hemoglobin disorder will be reported.

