9.8 Blood and human milk processing and analysis

Biological samples will be collected in the village (woman's home, or central village location such as the village chief's home), placed on ice, and transported to the field lab in Kampong Thom within 5 hours of collection. Phlebotomists will collect 9 mL venous blood from mothers and 5 mL from infants (in EDTA-coated Vacutainers). Venous blood samples will be processed as per **Figure 2**. All samples will be stored at -20°C for <1 week before being transported the National Institute for

Public Health Laboratory in Phnom Penh for storage at -80°C . Samples will be batch shipped on dry ice after the 24 weeks postnatal data collection is completed.

[figure not shown]

Figure 2: Processing protocol for venous blood and breast milk samples.

Venous blood samples will undergo analysis for both transketolase activity and thiamine diphosphate concentrations, as described in *3.3 Biomarkers of thiamine status*, by [name] at the NIHR BRC Nutritional Biomarker Laboratory at the University of Cambridge in the United Kingdom. At 2 weeks postnatal, maternal whole blood ThDP and erythrocyte transketolase activity will be measured. At 24 weeks postnatal, ThDP and transketolase activity will be measured in both whole blood and erythrocytes, and infant samples will be assayed for whole blood ThDP and erythrocyte transketolase activity. When ThDP is assessed in whole blood, concentrations must be normalized to hemoglobin concentrations and/or hematocrit (47). Therefore, hemoglobin concentration and hematocrit will be measured on all whole blood samples via a HemoCue 201 portable hemoglobinometer and capillary hematocrit tubes, respectively.

Evidence from the 2014 Cambodian National Micronutrient survey indicates that eThDP is affected by the presence/absence of genetic hemoglobin disorders. With this, it is vital to assess the presence/absence of genetic hemoglobin disorders, as this could influence participant's response to thiamine, it may influence transketolase, and it could change thiamine dosage requirements in other

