- Secondary analyses: First, fit an Emax curve using nonlinear least squares approach allowing curve to vary by presence/absence of genetic hemoglobin disorder. Estimates of the dose that reaches 90% concentration by genetic hemoglobin disorder status will be reported following evidence from the global test. Second, test for a treatment effect using linear regression and estimate a difference in mean concentration. Third, test for a treatment effect using linear regression with treatment group and treatment by genetic hemoglobin disorder interaction. Treatment effects (difference in mean concentration) will be estimated separately by genetic hemoglobin disorder where the relevant interaction term has a p-value <0.05. Pairwise comparisons will be reported following evidence of a treatment group effect (see Section 5.8). Fourth, test for a linear relationship using linear mixed effects model with CRP at 2 and 24 weeks postnatal, time and treatment group as predictors. Estimate of the mean change (with 95% CI) in ThDP for one unit increase in CRP will be reported. Fifth, test for a linear relationship using linear mixed effects model with AGP at 2 and 24 weeks postpartum, time and treatment group as predictors. Estimate of the mean change (with 95% CI) in ThDP for one unit increase in AGP will be reported.
- Adjustment: Maternal ThDP at 2 weeks postpartum, health centre (linear regressions and mixed effects models only)

7.3.5 *Maternal transketolase activity coefficient (24 weeks)*

- Outcome: Continuous outcome of maternal TKac at 24 weeks postpartum.
- Primary analysis: Fit an Emax curve using nonlinear least squares approach. Estimate of the dose that reaches 90% concentration (with 95% CI) will be reported.

- Secondary analyses: First, fit an Emax curve using nonlinear least squares approach allowing curve to vary by presence/absence of genetic hemoglobin disorder. Estimates of the dose that reaches 90% concentration by genetic hemoglobin disorder status will be reported following evidence from the global test. Second, test for a treatment effect using linear regression and estimate a difference in mean TKac. Third, test for a treatment effect using linear regression with treatment group and treatment by genetic hemoglobin disorder interaction. Treatment effects (difference in mean TKac) will be estimated separately by genetic hemoglobin disorder where the relevant interaction term has a p-value <0.05.

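### The global hemoglobin-disorder test in SAP 7.1 counts a plain level difference as effect modification, and cleanly answers neither whether the response to thiamine differs nor whether the target dose differs

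*Combined protocol and SAP*

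**What the plan says.** SAP 5.7 gives the purpose of the hemoglobin-disorder analyses of maternal and infant ThDP and TKac as testing for effect modification. SAP 2.2 asks whether the target dose for those outcomes depends on disorder status.

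For the dose-response part, SAP 7.1 says that coefficients for the disorder "will be added to all parameters of the Emax curve": β on E0, γ on Emax, α on ED50 and δ on h. It then says that "Evidence of curve shape differences between presence or absence of genetic hemoglobin disorder will be determined by global Likelihood ratio tests". If that test gives P < 0.05, separate target doses are reported with and without the disorder. Single-coefficient tests follow a significant global test, but no rule ties reporting to them. Sections 7.3.1 and 7.3.3 to 7.3.5 repeat the trigger for each outcome. The target is defined as the dose at which the curve reaches 90% of E0 + Emax. The covariate adjustments listed in 7.3 do not apply to the Emax fits.

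For the group comparisons of maternal ThDP and TKac, SAP 7.3.4 and 7.3.5 say to "test for a treatment effect using linear regression with treatment group and treatment by genetic hemoglobin disorder interaction". No disorder main effect is listed.

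Protocol 9.8 reports that national survey evidence "indicates that eThDP is affected by the presence/absence of genetic hemoglobin disorders". For transketolase it says only that the disorder may have an influence.

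**The concern.** A difference in E0 alone means that one group sits higher or lower at every dose and gains exactly the same from each dose. That is neither a difference in curve shape nor effect modification. But β is absent from the null model and present in the alternative, so a level difference alone can make the global test significant. The main effect and the interaction are tested as one.

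The documents lead one to expect such a level difference for erythrocyte ThDP, and nothing in the unadjusted Emax fits absorbs it. The trial could then describe an ordinary main effect as a changed response to thiamine and print separate doses on the strength of it. Protocol 9.8 gives a possible change in dosage requirements in other countries as a reason for measuring the disorder, so readers may take the separate doses seriously.

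**Working it through.** **The plan's own figure.** The documents give no power or error rate for the disorder tests. The nearest stated figure is the sample size in SAP 3.6: 40 µg/L "in human milk total thiamine concentration between any two treatment groups with 90% power", SD 43 µg/L (the "estimated SD of control group in a Cambodian thiamine-fortified fish sauce trial"), and a "two-sided alpha of 0.0083 for each of the 6 pairwise comparisons between 4 treatment groups". A two-sample t-test (noncentral t) has power 0.897 at n = 37 and 0.906 at n = 38. SAP 3.6 adds: "This sample size allows for 20% attrition". So 38/0.8 = 47.5, or 48 per group, as stated. From the same section I take N = 320 planned and 320 × 0.8 = 256 after attrition.

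**What the global test detects.** SAP 7.1 writes the baseline as E0(1 + β·GD), where GD marks the disorder. Set α = γ = δ = 0. The group difference is then E0·β at every dose, and the gain over placebo, Emax·dose^h/(ED50^h + dose^h), is the same in both groups. The null α = β = γ = δ = 0 is still false whenever β ≠ 0.

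**How often it rejects for that reason alone.** Eight parameters describe eight dose-by-disorder cells, so the test is close to a joint F test of four within-dose differences on 4 and N − 8 df. With prevalence p in each arm and a shift of s SD, each arm of N/4 contributes (N/4)·p(1−p)·s². Hence λ = N·p(1−p)·s². The values of p and s are assumptions.

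| N | p | s | λ | P(reject) |
|---|---|---|---|---|
| 256 | 0.1 | 0.1 | 0.23 | 6% |
| 256 | 0.3 | 0.2 | 2.15 | 18% |
| 256 | 0.3 | 0.3 | 4.84 | 38% |
| 256 | 0.5 | 0.5 | 16.0 | 91% |
| 320 | 0.3 | 0.3 | 6.05 | 47% |
| 320 | 0.5 | 0.5 | 20.0 | 96% |

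**Check by simulation.** I simulated the actual nonlinear least-squares likelihood-ratio test, 600 trials per setting, with N = 256, p = 0.4 and the milk planning values as a stand-in.
- As written (4 df): rejection in 30–31% at 0.25 SD, 88–90% at 0.5 SD and 100% at 0.75 SD. The formula gives 30%, 89% and over 99%.
- With the E0 shift in both models and 3 df for α, γ, δ: 2.8–5.7% for every shift from 0 to 0.75 SD. The rate also stays near 5% if h is shared.

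**What a level shift does to the target dose.** Setting 0.9(E0 + Emax) = E0 + f·Emax gives f = 0.9 − 0.1·E0/Emax and dose = ED50·[f/(1−f)]^(1/h). The documents give no ThDP or TKac means, so I use the SAP 3.6 milk values for illustration: E0 = 136, Emax = 210 − 136 = 74, ED50 = 1.2, so f = 0.9 − 13.6/74 = 0.716. The planning text fits h = ln(0.716/0.284)/ln 2 = 1.34 if 90% of the total is reached at 2.4 mg/d, or h = ln 9/ln 2 = 3.17 if 90% of the effect is.

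| Shift in E0 | f | Target, h = 1.34 | Target, h = 3.17 |
|---|---|---|---|
| −43 µg/L (−1 SD) | 0.774 | 3.02 mg/d | 1.77 mg/d |
| −21.5 (−0.5 SD) | 0.745 | 2.68 | 1.68 |
| 0 | 0.716 | 2.40 | 1.61 |
| +21.5 (+0.5 SD) | 0.687 | 2.16 | 1.54 |
| +43 (+1 SD) | 0.658 | 1.96 | 1.48 |

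The dose giving 90% of Emax, ED50·9^(1/h), stays at 6.22 or 2.40 mg/d throughout.

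**The regressions, read literally.** Treatment plus treatment-by-disorder with no main effect gives four within-arm disorder differences. At N = 256 and 0.5 SD, before baseline adjustment, each has expected z = 0.5·√(64·p(1−p)) = 1.83 to 2.00 for p = 0.3 to 0.5. Each is then significant with probability 45–52%. At least one of four is significant with probability 1 − (1−0.450)⁴ = 91% to 1 − (1−0.516)⁴ = 95%. With the main effect stated, the 3-df interaction test holds 5%.

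**The case against.** The strongest reply is that the SAP's target depends on E0 by definition. SAP 2.2 asks whether that dose varies with disorder status, and an E0 shift alone makes it vary, so E0 belongs in a test of that question. This stands. A reader might infer that every rejection under a level shift is a false positive, or that the trial would report different doses where none exist. The documents do not support that reading. A rule that released separate doses only on evidence about Emax and ED50 would hide real differences in the dose as the SAP defines it. But the reply does not rescue the test as evidence of effect modification or of a different curve shape, which is what the SAP says it measures.

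Five further replies have weight.

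- The single-coefficient tests could show that only β differs. They inform a careful reader, but they do not control what is reported.
- The movement in dose is modest. On the milk values, ±0.5 SD moves the target by under 0.3 mg/d, against the ±1.29 mg/d that SAP 3.6 gives for the whole sample.
- The cited evidence concerns erythrocyte ThDP and gives no size. Infant ThDP is measured in whole blood. A reader might infer an established main effect on all four outcomes, but Protocol 9.8 does not say so.
- The missing main effect in the regressions may be shorthand, and adjustment for the 2-week value would absorb part of a stable difference.
- Having as many parameters as dose cells is not peculiar to this test. The primary fit also has four parameters on four doses.

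**Conclusion.** The point holds for the global test. It is described as evidence of effect modification, but a level difference alone can drive it. When Emax, ED50 and h are equal, it rejects in about 38–96% of trials for prevalence 30–50%, shift 0.3–0.5 SD and 256–320 women. For prevalence 10–30%, shift 0.1–0.2 SD and 256 women, the figure is 6–18%. Prevalence and shift are assumptions throughout.

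These are excess rejections for the question of effect modification. They are not all errors for the question of the target dose, which moves with E0. The defect is that one P value stands in for two questions and settles neither.

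The regression wording is a minor point that depends on a literal reading. All of this concerns secondary analyses, to which SAP 5.8 gives less weight. The primary milk outcome has no disorder test and is unaffected. The change is worth making because it costs little and the result could be misread.

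**What to change.** 1. **Effect modification (SAP 7.1).** Put the disorder shift in E0 in both the null and the alternative model, and test α, γ and δ jointly on 3 df. Sharing h and testing α and γ on 2 df is optional. It assumes a common Hill factor.
2. **Target dose by disorder status (SAP 2.2 and 7.1).** Estimate the between-group difference in the SAP-defined dose directly, with a bootstrap confidence interval, and base the conclusion on that rather than on the global P value. State that this difference can come from E0 alone, or also report the dose giving 90% of Emax, which does not depend on E0.
3. **Regressions (SAP 7.3.4 and 7.3.5).** Write the model as treatment + disorder + treatment-by-disorder, with a 3-df interaction test.

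The cost is SAP wording, a little more analysis and fewer degrees of freedom in the interaction test. No new data are needed.
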